# 329 13.1 General principles

- 330 13.1.1 The primary and secondary outcomes will be analyzed in an intention-to-treat
- population, i.e., all patients are analyzed in the group to which they are randomized. Also, we
- will do per-protocol analysis for the primary endpoints after excluding patients with major
- 333 protocol deviation.
- 334 13.1.2 For continuous variables, the Kolmogorov-Smirnov test will be applied to evaluate the
- distribution. Variables with normal distribution were presented as mean  $\pm$  standard deviation
- 336 (SD). Variables with non-normal distribution will be presented as median and interquartile
- 337 range (IQR).
- 13.1.3 Categorical variables will be presented as number of cases (%).
- 13.1.4 For the primary outcomes, p<0.025 (0.05/2) will be considered statistically significant.
- For other outcomes, two-tailed tests will be used and p<0.05 will be considered to be
- statistically significant unless otherwise indicated after Bonferroni correction.

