#### 3.2 Sample size calculation

Based on a pilot study, we suppose that the mean difference in NRS pain score immediately after fetal delivery (10 min after administering esketamine) would be 0.3 with standard deviations (SD) of 0.85 and 1.23, respectively, between the two groups. With alpha set at 5% and power at 90%, 263 patients will be needed in each group. Considering a drop-out rate of about 10%, we plan to enroll 300 patients in each group. The sample size was estimated with the PASS 15.0 software.

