## 119 4. Study participants

- Potential participants will be screened before surgery by the qualified investigators.
- 121 4.1 Inclusion criteria
- 4.1.1 Women aged 18 years or older.
- 4.1.2 Full-term single pregnancy.
- 4.1.3 Scheduling for elective caesarean delivery.
- 4.1.4 Planning for epidural anesthesia.
- 4.1.5 Agree to participate, and give signed written informed consents
- 127 4.2 Exclusion criteria
- Patients will be excluded if they meet any of the following criteria:
- 129 4.2.1 Body mass index (BMI)  $\geq$ 27 kg/m^2.
- 4.2.2 Previous mental illness; central nervous system disease; liver disease, abnormal kidney
- function; abnormal heart and lung function; diabetes; American Society of Anesthesiologists
- 132 (ASA) classification III or above.
- 4.2.3 Severe obstetric complications, such as preeclampsia and eclampsia, pregnancy-induced
- hypertension, placenta previa, or placental abruption.
- 4.2.4 Stillbirth, neonatal malformation.
- 4.2.5 Contraindications to epidural anesthesia, including abnormal coagulation function, taking
- anticoagulant therapy, severe hypovolemia, or hemodynamic instability.
- 138 4.3 Criteria of drop-out
- 139 4.3.1 Study intervention is not administered (change to general anesthesia) or protocol
- 140 deviation occurs.
- 4.3.2 Intervention interrupted by the investigators/anesthesiologists (due to adverse events).
- 142 4.3.3 Use of a prohibited drugs.
- Details of the above situations should be recorded and corrected when possible. The cases will
- be followed up according to the study protocol and included in the intention-to-treat analysis.
- 4.3.4 Withdraw consent after intervention started.
- The situation should be recorded. The primary therapeutic effects recorded in the last time will
- be regarded as the final assessment results. The cases will be included in the intention-to-treat
- 148 analysis.
- 149 **4.4** Criteria of elimination
- Enrolled patients will be excluded if they meet any of the following criteria:

- 4.4.1 Withdraw consents before intervention.
- 4.4.2 Surgery cancelled.
- 4.4.3 No assessment result of the primary outcomes.
- The causes of elimination should be explained. The case will be excluded from the intention-
- to-treat analysis. The case report forms will be preserved for reference.

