#### 355 13.5 Efficacy analysis

356 13.5.1 Evaluation of primary endpoints

- For the primary outcomes (maternal pain intensity and sedation score immediately after fetal
- delivery), the differences between group will be analyzed using Mann-Whitney U test. Median
- differences and 95% CIs will be calculated with the Hodges-Lehmann estimators.
- 360 13.5.2 Evaluation of secondary and other endpoints
- 361 13.5.2.1 Discrete variables (maternal pain intensity and sedation score during the perinatal
- period, neonatal Apgar scores, and umbilical vein pH) will be analyzed with the Mann-Whitney
- 363 U tests. Median differences and 95% CIs will be calculated with the Hodges-Lehmann
- 364 estimators. Missing data will not be replaced.
- 13.5.2.2 Categorical variables (neonatal ward admission proportion) will be analyzed using the
- chi-square tests, continuity correction chi-square tests or Fisher exact tests. The rate differences
- and 95% CIs will be provided. Missing data will not be replaced.
- 368 13.5.2.3 Time-to-event variables (length of hospital stay after surgery) will be analyzed with
- the Kaplan-Meier estimators with differences between groups assessed by the log-rank test;
- Cox proportional hazards models will be used to calculate HRs and 95% CIs.
- 371 13.6 Safety analysis
- 372 13.5.1 Describe the occurrence of adverse events in each group.
- 13.5.2 Describe the management of adverse events when appropriate.
- 374 13.5.3 Describe the occurrence of severe adverse events.
- 375 13.5.4 The rates of adverse events and/or managements between the two groups will be
- compared with Chi-Square test, continuity correction Chi-Square test or Fisher exact test.
- 377 13.5.5 Missing data will not be replaced.

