# 4. Statistical analysis

# 530 4.1 General principles

- 4.1.1 The primary and secondary outcomes will be analyzed in an intention-to-treat population,
- i.e., all patients are analyzed in the group to which they are randomized. Also, we will do per-
- protocol analysis for the primary endpoints after patients with major protocol deviation.
- 534 4.1.2 For continuous variables, the Kolmogorov-Smirnov test will be applied to evaluate the
- distribution. Variables with normal distribution were presented as mean  $\pm$  standard deviation
- 536 (SD). Variables with non-normal distribution will be presented as median and interquartile
- range (IQR).
- 538 4.1.3 Categorical variables will be presented as number of cases (%).
- 4.1.4 For the primary outcomes, p<0.025 (0.05/2) will be considered statistically significant.
- For other outcomes, two-tailed tests will be used and p<0.05 will be considered to be
- statistically significant unless otherwise indicated after Bonferroni correction.

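### Rule 4.4.3 drops a newborn's Apgar scores and cord pH when the mother has no primary-outcome score, and no population is stated for the other harm data

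*Combined protocol and SAP*

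**What the plan says.** - **Populations.** Protocol 13.1.1: "The primary and secondary outcomes will be analyzed in an intention-to-treat" population, with a per-protocol analysis added for the primary endpoints only. SAP 4.1.1 has the same: "The primary and secondary outcomes will be analyzed in an intention-to-treat population". Neither document defines another population.
- **Elimination.** Protocol 4.4: "Enrolled patients will be excluded if they meet any of the following criteria". The third criterion reads "4.4.3 No assessment result of the primary outcomes". The section goes on to say that such a case leaves the intention-to-treat analysis, that the cause must be explained, and that the forms are kept for reference. The SAP does not repeat these rules.
- **Drop-out.** Protocol 4.3.1 to 4.3.3 cover undosed women, protocol deviations, interruption for adverse events and prohibited drugs. These women are followed up and stay in the intention-to-treat analysis. Under 4.3.4, women who withdraw consent after the intervention has started also stay in, with their last recorded value.
- **Outcomes.** The co-primary outcomes (8.1) are the NRS pain score and the Ramsay sedation score just after delivery, about 10 minutes after the drug. Apgar scores and umbilical vein pH are secondary (8.2.3, 8.2.4). Haemodynamics and neonatal ward admission are other outcomes (8.3).
- **Safety.** Protocol 13.6 and SAP 4.6: "Describe the occurrence of adverse events in each group", followed by a between-group test of the rates. No denominator is given.

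**The concern.** A missing primary score is an event after dosing. A woman who has a severe reaction, or who is converted to general anaesthesia between the injection and delivery, is more likely than others to have no score. If a missing score removes the whole case, membership of the analysis set depends on something the drug can cause.

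For the pain and sedation comparisons this is a familiar missing-data problem. The further difficulty is that the rule removes the case and not just the missing value, so it reaches outcomes that were measured. A newborn's Apgar scores and cord pH do not need the mother's pain score, yet they go with it. The loss would tend to fall on newborns of mothers with difficult courses, and in a direction that makes the drug look safer. The background section names maternal and fetal outcomes among the things the trial will explore, so this touches a stated aim.

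**Working it through.** **1. The plan's own figure, to see whether it is affected.** The inputs in protocol 3.2 are a difference that "would be 0.3 with standard deviations (SD) of 0.85 and 1.23, respectively, between the two groups", with 5% alpha and 90% power. Taking alpha as two-sided:

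n per group = (1.960 + 1.282)² × (0.85² + 1.23²) / 0.3² ≈ 10.507 × 2.2354 / 0.09 ≈ 261.

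The unequal-variance t calculation gives 263, as stated. With 10% drop-out, 263 / 0.90 = 292.2, so 293; and 300 × 0.90 = 270, which exceeds 263. Nothing in this point changes the 263 or the 300.

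**2. Which elimination rule can reach a dosed woman?** Rule 4.4.1 is withdrawal before the intervention and 4.4.2 is cancelled surgery. Only 4.4.3 can act after dosing. The drug is given about 2 minutes before incision (6.1.6) and the primary scores are taken about 10 minutes after it (8.1), so there is a post-dose interval in which scoring can be prevented.

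**3. Which outcomes go with her?**

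| Outcome | Class | Population stated | Effect of 4.4.3 |
|---|---|---|---|
| NRS, Ramsay at delivery | Primary | Intention-to-treat | Removed; at least one value is missing anyway |
| Apgar, umbilical vein pH | Secondary | Intention-to-treat | Removed, even if measured |
| Haemodynamics, neonatal admission | Other | None | Open |
| Adverse and severe adverse events | Safety | None | Open |

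The second row follows from the text as written. The last two rows do not: 4.4 takes the case out of the intention-to-treat analysis, and no text ties those outcomes to it.

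The deletion is also unnecessary for the neonatal outcomes. Protocol 13.5.2.1 already says that missing data will not be replaced, so a missing maternal score could be left missing without touching a measured Apgar score.

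**4. Where the rules collide.** A dosed woman whose intervention is interrupted for an adverse event and who has no score meets 4.3.2 (followed up, kept) and 4.4.3 (removed). No precedence is given. Since the injection takes 1 minute, a reaction after it may not count as an interruption at all; then 4.4.3 may be the only rule that applies.

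**5. One score or two?** There are two co-primary scores, and 4.4.3 does not say whether one or both must be missing. A woman too sedated to give an NRS can still have a Ramsay score, whose level 6 describes a patient who does not respond. She stays in under one reading and is removed under the other.

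**6. What a few losses could do.** The documents give no rates, so every count here is assumed. Suppose the exclusion were carried over to a yes/no harm, and only event cases in the esketamine arm were lost (two-sided Fisher test, 300 per arm at the start):

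| Full data | p | Lose 1 | Lose 2 | Lose 5 |
|---|---|---|---|---|
| 6 vs 0 | 0.0305 | 0.0305 | 0.0610 (4/298) | 0.4958 (1/295) |
| 10 vs 2 | 0.0367 | 0.0367 | 0.0626 (8/298) | 0.2825 (5/295) |
| 30 vs 15 | 0.0290 | 0.0290 | 0.0404 (28/298) | 0.1026 (25/295) |

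In the first row the observed rate falls from 2.0% to 1.7%, 1.3% and 0.3%. The unchanged p after one loss reflects the discreteness of the two-sided Fisher test: once the arms differ in size, the mirror-image table in the other tail becomes slightly more probable and is no longer counted.

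For Apgar and pH the planned test is Mann-Whitney, so these figures do not carry over directly. There, 1 to 5 newborns lost is 0.3% to 1.7% of an arm (1/300 to 5/300).

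**The case against.** The strongest reply is that 4.4 does not remove maternal harms at all. A reader might infer that dosed women with the worst reactions leave the adverse-event comparison. The documents do not support that. The exclusion is from the intention-to-treat analysis, 13.1.1 applies that set only to primary and secondary outcomes, and 13.6 describes events by group without that restriction. This stands. An unstated denominator is not an exclusion, and by itself it would be only a missing detail.

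Second, the plan retains many of the women in question. Rule 4.3.2 keeps those interrupted for adverse events, 4.3.1 keeps deviations, and 4.3.4 keeps those who withdraw after the intervention has started. This also stands, and it narrows the point to dosed women with no score. It does not settle their status, because 4.4.3 applies to the same women.

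Third, severe events cannot vanish unseen. They are reported in writing within 24 hours (10.3), described separately (13.6) and checked against source (14.2.4.7). Elimination causes are explained, and elimination and drop-out are compared between groups (13.2). That protects case reporting. It does not put a newborn's Apgar score back in the comparison, and 13.2 compares an overall rate, in which a few informative losses would be hard to see.

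Fourth, triggering cases are probably rare, especially if both scores must be missing, and any numerical illustration rests on invented counts. This is fair.

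**Conclusion.** The point holds in a limited form. As written, 4.4.3 removes measured Apgar scores and umbilical vein pH when the mother has no primary-outcome score, including when she was dosed. For maternal adverse events, severe adverse events, haemodynamics and neonatal admission, the same exclusion is possible but not written. Two ambiguities add to this: the conflict between 4.3 and 4.4.3, and whether one or both missing scores count.

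The size of the effect is unknown and probably small. The illustration shows only that two to five one-sided losses could alter a rare-harm comparison; it is not evidence that such losses will occur. The conclusion rests on reading 4.4.3 literally and on unscored women being more likely to have had a difficult course, which is plausible but not documented. The sample size and, beyond the one-or-both question, the primary pain and sedation comparisons are not at issue here.

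**What to change.** Amend protocol 4.4, 13.1 and 13.6, and SAP 4.1 and 4.6, to state:

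1. Rule 4.4.3 limits only the pain and sedation analyses and applies to each co-primary score separately. A woman with a Ramsay score and no NRS is in the sedation analysis and not in the pain analysis.
2. Adverse events, severe adverse events, haemodynamics, Apgar scores, umbilical vein pH and neonatal admission are analysed in every randomised woman who received any amount of study drug, and her newborn, whether or not a primary score exists. Say that women are grouped by the drug received.
3. How 4.3 and 4.4.3 fit together for a dosed woman with no score. Copy the result into the SAP, which at present does not contain the 4.4 rules.

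The sentence in 13.1.1 and SAP 4.1.1 that places all secondary outcomes in the intention-to-treat set needs a matching exception.

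The cost is wording. No new measurements are needed, provided that data collection continues for women who meet 4.4.3; section 4.4 should say so, since follow-up is promised only for 4.3.1 to 4.3.3. The small downside is that neonatal outcomes are reported in a set slightly different from the efficacy set, without the undosed women whom 4.3.1 keeps there.

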# 165 5. Randomization and Masking

### 166 5.1 Randomization

- 5.1.1 Random allocations will be generated using the SPSS 22.0 (IBM Corp, Armonk, NY,
- 168 USA) in a 1:1 ratio. Assignments will be concealed in sequentially numbered opaque envelops.
- 5.1.2 For each participating center, a study coordinator will be designated to distribute the
- 170 randomization result to the anesthesiologists according to the sequence of recruited patients,
- and to coordinate between investigators.
- 5.1.3 For each recruited patient, an anesthesiologist will be designated for anesthesia and data
- 173 collection according to the result of randomization.
- 5.1.4 Study intervention (use esketamine or normal saline) will be provided according to the
- randomization results by anesthesiologists who do not participate in the outcome assessments.

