# 251 8.1 Primary outcome

- Our co-primary outcomes include maternal pain intensity and sedation score immediately after
- fetal delivery (about 10 min after esketamine). Pain intensity will be assessed with the NRS.

- 254 Maternal sedation level will be assessed with the Ramsay Sedation Scale.
- 255 **8.2 Secondary outcomes**
- 8.2.1 Maternal pain intensity as assessed with the NRS at the following timepoints: surgical
- 257 incision (2 min after study drug administration), 5 min after study drug administration, end of
- surgery, 6 h after surgery, and 12 h after the surgery.
- 8.2.2 Maternal sedation level as assessed with the Ramsay Sedation Scale at the following
- 260 timepoints: surgical incision (2 min after study drug administration), 5 min after study drug
- administration, end of surgery, 6 h after surgery, and 12 h after the surgery.
- 262 8.2.3 Neonatal Appar score assessed at 1 and 5 minutes after birth.
- 263 8.2.4 Postnatal umbilical vein blood gas pH value.
- 264 8.3 Other outcomes
- 8.3.1 Mean blood pressure (MBP), heart rate (HR), and pulse oxygen saturation (SpO2)
- 266 measured before anesthesia, immediately after anesthesia, surgical incision (2 min after study
- drug administration), 5 min after study drug administration, immediately after fetal delivery
- 268 (10 min after study drug administration), end of surgery, and 1 h after surgery.
- 269 8.3.2 The requirement of neonatal ward admission and length of hospital stay.
- 270 8.3.3 Plasma concentrations of esketamine in maternal blood, neonatal umbilical venous blood
- and umbilical arterial blood after birth.

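### Testing each of the two primary outcomes at a fixed 0.025 is valid but inefficient: Holm's procedure keeps the same 5% family-wise error and never rejects less

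*Combined protocol and SAP*

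**What the plan says.** Protocol 8.1 and SAP 3.1 name two primary outcomes at one time point: "Our co-primary outcomes include maternal pain intensity and sedation score immediately after" fetal delivery. Protocol 13.5.1 and SAP 4.5.1 test each with its own Mann-Whitney U test and report a Hodges-Lehmann estimate with a 95% interval for each.

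The threshold is in protocol 13.1.4 and SAP 4.1.4: "For the primary outcomes, p<0.025 (0.05/2) will be considered statistically significant". The next sentence covers the remaining outcomes: "For other outcomes, two-tailed tests will be used and p<0.05 will be considered to be" "statistically significant unless otherwise indicated after Bonferroni correction". No stepwise, hierarchical or alpha-passing rule is given for the primary pair. Nothing states in words whether one success is enough or both are needed.

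The sample size (protocol 3.2, SAP section 2) rests on pain alone. The mean difference "would be 0.3 with standard deviations (SD) of 0.85 and 1.23, respectively, between the two groups", and "With alpha set at 5% and power at 90%, 263 patients will be needed in each group". No effect, spread or power is given for sedation.

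**The concern.** Under a fixed split, the 0.025 assigned to one outcome stays with it even after that outcome has succeeded. If sedation is significant at 0.025 and pain has p = 0.03, the plan calls pain non-significant. Holm would declare pain significant at the same overall 5% error rate. The same applies with the outcomes exchanged.

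At stake is the power of whichever outcome has the larger p-value. This matters most for pain, because it is the only outcome on which the trial is sized.

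**Working it through.** **Inputs.** Difference 0.3 and SDs 0.85 and 1.23 (protocol 3.2); 263 per group analysed and 300 enrolled (protocol 3.2); 1:1 allocation (protocol 5.1.1); threshold 0.025 per outcome (protocol 13.1.4). *Assumed:* two-sided primary tests, since the plan states two-tailed testing only for the other outcomes; sedation power at 0.025 from none to 99%; correlation of 0 or 0.3 between the two test statistics.

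**1. The plan's own figure.** The sum of variances is 0.85² + 1.23² = 2.2354. The normal formula gives n = (1.960 + 1.2816)² × 2.2354 / 0.3² ≈ 261 per group. An unequal-variance t calculation gives 263, so the plan's number is reproduced at two-sided 0.05.

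**2. Error control.** The split totals 0.025 + 0.025 = 0.05, or 1 − 0.975² = 0.0494 if the tests are independent. Testing both at 0.05 with a claim for either would give up to 1 − 0.95² = 0.0975 under independence. The split therefore does real work. Holm compares the smaller p-value with 0.025 and, only if that passes, the larger with 0.05. It also holds family-wise error at 5%, and it rejects everything that the split rejects.

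**3. Pain power at 263 per group.** The noncentrality is 0.3 / √(2.2354/263) = 3.254.
- At 0.05: Φ(3.254 − 1.960) = 90.2%.
- At 0.025: Φ(3.254 − 2.241) = 84.4%.
- Difference: 5.78 points.

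**4. Holm's gain for pain.** Holm adds the cases in which pain falls between 0.025 and 0.05 and sedation has passed 0.025. With independent statistics:

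Holm pain power = 84.44% + 5.78 points × (sedation power at 0.025)

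| Sedation power at 0.025 (assumed) | Fixed split | Holm, correlation 0 | Holm, correlation 0.3 |
|---|---|---|---|
| No effect (0.025 rejection rate) | 84.4% | 84.6% | – |
| 50% | 84.4% | 87.3% | 86.5% |
| 80% | 84.4% | 89.1% | 88.5% |
| 90% | 84.4% | 89.6% | 89.3% |
| 99% | 84.4% | 90.2% | 90.1% |

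At 270 per group (300 less 10%), the values at 0.05 and 0.025 are 90.9% and 85.4%. The largest possible gain is then 5.5 points.

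**5. What Holm leaves unchanged.** The chance of at least one success is the same, because both rules require the smaller p-value to pass 0.025. With sedation at 90% and independence it is 1 − (1 − 0.844) × (1 − 0.90) = 98.4% under either rule. The chance of claiming both outcomes does change in that case, from 0.844 × 0.90 = 76.0% to 84.7%.

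**6. If both had to succeed.** Testing each at 0.05 would keep the overall error at or below 5% with no split. In the same case joint power is 0.902 × 0.941 = 84.9%, where 94.1% is sedation's power at 0.05, against 76.0% with each at 0.025.

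**The case against.** The strongest reply is that the rule is pre-specified, simple and valid, so preferring Holm is a matter of efficiency. That stands. A reader might infer that the split gives power away for nothing. The documents do not support this: where either outcome can carry a claim, the split buys 5% family-wise control, and Holm adds nothing to the chance of at least one success.

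A reader might also take the label co-primary to mean that both outcomes must succeed, which would make the split unnecessary. The division by two points the other way, and each outcome has its own test and estimate. The wording favours separate claims, although it does not say so.

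The gain also depends on sedation. It is tempting to say that a sedation difference is the easier result to show against saline, but the documents give no sedation figures, and with no sedation effect the gain almost vanishes.

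Nor should the gain be valued as 310 − 263 = 47 women per group. Those are the unequal-variance sizes for 90% pain power at 0.025 and 0.05. Holm approaches that difference only if sedation is almost certain to pass, and the figure belongs to the separate mismatch between the sizing alpha and the testing alpha.

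Finally, a reader might fear that success on sedation alone would be presented as analgesic success. The stated purpose covers sedative and analgesic effects alike, and nothing in the plan lets a sedation result support an analgesia claim.

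In favour of Bonferroni, its usual convenience is a simple set of matching simultaneous intervals. The plan does not use it: it reports 95% intervals for the primary outcomes, whereas a 0.025 test corresponds to 97.5%.

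**Conclusion.** The fixed split is valid but inefficient, and replacing it is a cheap improvement. That Holm never rejects less needs no assumption about effect sizes or about the test used. The size of the benefit does: about 0 to 6 points of pain power from a base of about 84.5% at 263 per group, governed by an unknown sedation power. The figures use two-sided normal approximations and the plan's difference and SDs. They are not Mann-Whitney power on an 11-point pain scale and a six-level sedation scale, where ties are likely.

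The point is separate from the alpha mismatch. Correcting the 5% used for sizing would leave the fixed split in place, and adopting Holm would not guarantee 90% power for pain.

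**What to change.** In protocol 13.1.4 and SAP 4.1.4, replace the fixed threshold with wording such as: *The two primary outcomes will be tested by Holm's procedure at an overall two-sided level of 0.05. The smaller p-value is compared with 0.025 and, if it passes, the larger is compared with 0.05. A separate claim is made for each outcome that passes.* If the sponsor instead intends that both outcomes must succeed, state that and test each at 0.05.

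Either change is a short edit, made before unmasking, and needs no new data or participants. The one drawback of Holm is that the confidence level matching the second outcome's test depends on the step reached, so the plan should say which intervals will be reported.
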